#### **BP monitoring: uAOBP, central BP, and home BP**

Firstly, BP will be taken simultaneously from both upper arms by an oscillometric BP monitor (WatchBP Office Central; Microlife AG, Widnau, Switzerland). Subjects with SBP Differences between both arms more than 5 mmHg will be excluded. The performance of BP measurements will be adhered to the standard BP measurements procedures. For the uAOBP and CBP, the measurements will be conducted in a quiet room without the presence of clinical personnel. Patients will be seated in a quiet room without talking and taken as an average of 3 measurements with an automated device (HEM-907, Omron Healthcare, Lake Forest, IL) that has been preset to wait 5 minutes before measurements. Simultaneously, the central BP will be measured in the other upper arm. (WatchBP Office Central; Microlife AG, Widnau, Switzerland). The determination of the right or left upper arm for uAOBP or central BP will be made in a random order by computer generated random codes before the enrollment. As for the home BP measurements, a validated device (WatchBP Home; Microlife AG, Widnau, Switzerland) will be provided for all subjects allocated to the home BP arm to measure their BP at home. Subjects are requested to take BP in the morning (within 2 hours after awakening) and afternoon before meals for 7 consecutive days before the scheduled clinical visits. BP in the first day of the measurements will be discarded and an average of home BP (all BP reading and BP in the morning and in the afternoon) will be generated and provided

for clinicians to guide their treatment. The ambulatory BP of all subjects will be measured at baseline, at 3 months, and at the end of the study by a validated device (WatchBP O3 AFIB Ambulatory). Similarly, the choice of right or left arm for the measurement of ambulatory BP will be determined in a random manner. All the automated BP readings are stored digitally for analysis and corresponding BP values in each arm will be provided for clinicians to guide their hypertension management.

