### **Study protocol**

Patients will be randomized to have hypertension management decisions made on the basis of the uAOBP, home BP, and central BP monitoring. Randomization will be done by using computer-generated randomization codes in 2 strata with baseline systolic BP (uAOBP) 130-155 mmHg and 155-180 mmHg. The BP measurements on left or right arm will also be determined by randomization codes.

To guide the management of hypertensive patients, medication adjustment will be made based on a published guideline with the measured BP through different BP monitoring methodologies. The use of different devices to obtain BP for guiding the care of hypertensive patients is aimed to determine whether these BP monitoring may be of comparable clinical value in routine practice. To achieve this, intervention patients will have medications titrated to normalize these different BP values. The target BP level, SBP 130 mmHg, of these different BP monitoring strategies are based on the latest guideline.

An overview of study protocol and acquired measures is presented in Table 1.

Although we encourage the adjustment of medication being adhered to the practice guideline, the choice of drug adjustment will be left to the discretion of the patient's attending doctor. During the measurement periods of home BP monitoring, no medication adjustment is allowable to preserve the comparability between different BP values. On the scheduled visits, the corresponding BP will be measured before meeting doctors and provided for clinicians to adjust patients' medication according to practice guideline. In summary, if the measured SBP is well within the target BP without possible side effects caused by antihypertensive agents, no medication adjustment is required. If the differences between measured SBP and target BP is less than 20 mmHg, the suggested maximal dose adjustment is 1 drug. If the BP differences are above 20 and 40 mmHg, addition of 2 drugs (or single pill combination) or 3 drugs (or single pill combination) are suggested, respectively. If low BP (less than 90/70mmHg) or any possible drug related side effects was noted, cautious adjustment of antihypertensive will be done. The dose adjustment and any possible side effects will be recorded throughout the whole study conduct period.

A sub-study will be performed to test the level of agreement between different measured BP values.

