### **Randomization, Outcomes, and Masking**

Each patient will be randomly assigned, using a standard computer protocol at the General Clinical Research Center, Taipei Veterans General Hospital, Taipei, Taiwan, to intervention in a 1:1:1 ratio using sealed opaque envelopes (sequentially numbered). The study coordinator will oversee the enrollment and intervention assignment and keep allocation concealment. The Primary outcome is the change of 24 hour mean ambulatory SBP at 3 months. The secondary outcomes include the change of 24 hour mean ambulatory DBP at 3 months, decrease of left ventricular mass at 12 months, change of SBP/DBP measured by uAOBP monitoring, home BP monitoring, or central BP monitoring, change of quality of Life, change of medication count and side effects. Any possible treatment related side effects including hypotension, injurious fall, dizziness, electrolyte imbalance (serum Na <130meq/L, serum K > 5.5 or <3.0 meq/L), syncope, acute renal failure (increase in serum

creatinine > 1.5 times baseline, or increase in serum creatinine by  $\geq 0.3$  mg/dL), and bradycardia (heart rate <50 bpm detected by electrocardiogram) will be recorded and evaluated. The medication quantity will be determined by daily defined dose (DDD) calculated as per World Health Organization standard (the DDD is a system for exact quantification of drug amount and standardization to enable comparison across drug classes, eg,  $1 \times \text{DDD} = 150$  mg irbesartan or 5 mg amlodipine). The quality of life is assessed by the Bulpitt hypertension- specific questionnaire. Two-dimensional echocardiography will be obtained by Artida Echocardiograph (Toshiba Medical Systems Corporation, Tokyo, Japan) and end-diastolic left ventricular (LV) dimensions were used to calculate LV mass by an anatomically validated formula, and subsequently normalized body height The caring physicians will remain blinded to the allocation by providing them with the measured BP values through a standardized report form without the knowledge of the used BP monitoring devices. Except patient reported outcome and adverse events, the investigators and participants are blinded to all the above outcome variables (which will be calculated at the end of the study), and assessment of LV mass will be conducted on side-by-side images by a technician blinded to allocation.

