### **Data Analysis and Statistical Analyses**

Based on data from our previous work, sample size (84 participants per group)

was determined on the basis of noninferiority between 3 independent groups ( $\alpha=0.05$ ;  $\beta=0.20$ ; standard deviation of ambulatory BP 11 mmHg; mean difference and non-inferior margin 5 mmHg, drop rate 10%).

We will test the normality of all parameters using the Shapiro–Wilk test. Categorical data are shown as proportions. Continuous data as means and standard deviations (SD) or as medium and interquartile ranges will be presented when appropriate.

Data will be analyzed on all patients who received the allocated strategy by intention-to-treat analysis if possible. For continuous variables of LV mass index, 24-hour ambulatory BP, heart rate, and quality of life, analysis will be undertaken using linear regression, with the dependent variable calculated as change over time. We will analyze DDD medication data recorded at all visits by using mixed regression models to account for repeated measures on individuals over time, with outcome variables log-transformed to correct heteroskedasticity where necessary.

The back-transformed means and confidence intervals are presented. Recommendations on medication use at each visit were categorized as maintain, increase, decrease or cease. A log-multinomial regression model will be used to assess the group differences for each of these 3 arms, with clustering on individuals to account for repeated measures over time.  $\chi^2$  test will be used to determine the

relationship between categorical variables. Intra-class correlations and paired t-test are used to assess the agreements between different strategies. A data safety monitoring board will be convened to oversee the progress of the study conduct and data relating to safety issue.

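### If the home-BP report shows separate morning and afternoon averages, it would tend to reveal the arm to the treating physician

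*Combined protocol and SAP*

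**What the plan says.** All places are in the combined protocol and SAP.

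- **Home BP output** (BP monitoring: uAOBP, central BP, and home BP). Patients measure morning and afternoon for 7 days, the first day is dropped, and "an average of home BP (all BP reading and BP in the morning and in the afternoon) will be generated and provided" to clinicians to guide treatment. The device "will be provided for all subjects allocated to the home BP arm to measure their BP at home".
- **Clinic BP output** (same section). uAOBP is "taken as an average of 3 measurements with an automated device"; central BP is taken at the same time on the other upper arm.
- **What clinicians receive** (same section). The "corresponding BP values in each arm will be provided for clinicians to guide their hypertension management".
- **Masking** (Randomization, Outcomes, and Masking). Physicians stay blinded by "providing them with the measured BP values through a standardized report form without the knowledge of the used BP monitoring devices". The Abstract and the section on double-blind versus open-label design make the same claim.
- **Titration** (Study protocol). No change is required "if the measured SBP is well within the target BP" and there are no side effects; larger steps are suggested as the gap to 130 mmHg passes 20 and 40 mmHg. Even so, "the choice of drug adjustment will be left to the discretion of the" attending doctor.

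**The concern.** The report form is the only means that the protocol names for keeping physicians unaware of the monitoring method. Leaving the device name off works only if the values themselves do not give it away. A morning and an afternoon average can come only from measurement outside the clinic, so printing them would tell the physician that the patient is in the home arm.

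The treating physician is the person whose decisions the trial compares. A physician who knows the arm may titrate harder or more gently according to how far he or she trusts home readings. The primary outcome is recorded by an ambulatory device, so the route to it would run through treatment decisions and not through outcome measurement. Visits 1 to 3 (days 0, 30 and 60 in Table 1) precede the 3-month ambulatory reading. The analysis section also compares the arms on those decisions directly: "Recommendations on medication use at each visit were categorized as maintain, increase, decrease or cease".

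**Working it through.** The point disputes no figure in the plan, so the check consists of setting the provisions side by side.

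**1. What each arm can produce.**

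| Arm | Source of the value | Can it be split into morning and afternoon? |
|---|---|---|
| uAOBP | mean of 3 readings at one clinic sitting | no |
| Central BP | same sitting, other upper arm | no |
| Home BP | two times of day over 7 − 1 = 6 retained days, or 6 × 2 = 12 sessions | yes |

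**2. What the home-arm sentence means.** There are two readings.

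- *Three averages:* overall, morning and afternoon.
- *One pooled average:* the parenthesis only lists what goes into it. The singular noun favours this reading.

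Home readings are requested only in the morning and the afternoon, so all readings together already cover both. On the pooled reading, the words about morning and afternoon would add nothing. The three-average reading is therefore the more natural one, but the pooled reading cannot be excluded.

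**3. Does another provision remove the split?** The masking section says that the form is standardized and hides the device. It does not say that the split is left off or that the other arms carry matching fields. Neither the Abstract nor the section on double-blind design adds this.

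**4. Does it matter who measures at home?** The BP monitoring section gives the home device to the home arm. Table 1 lists Home BP at Visits 1 to 7 without naming an arm, and home BP change is a secondary outcome. Even if every patient measures at home, clinicians receive the values that correspond to the patient's own arm. A split on the form would still mark the home arm.

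**5. Which home value is the measured SBP?** The titration rule compares one SBP with 130 mmHg. Two examples with assumed values show why the fix should name it:

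- Morning 136, afternoon 122: overall (136 + 122)/2 = 129. The gaps to 130 are +6, −8 and −1 mmHg, so only the morning value calls for a step.
- Morning 154, afternoon 142: overall (154 + 142)/2 = 148. The gaps are +24, +12 and +18 mmHg, so the morning value suggests two drugs and the others at most one.

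These examples show that the choice can matter. They do not show how often it would, because the documents give no distribution of morning-afternoon differences.

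**The case against.** The strongest reply is that the masking section contains an express control aimed at exactly this risk, and that a parenthesis should not outweigh it. A leak requires that the split be printed and be recognizable as such, and nobody can tell that without the form. This stands in part: it makes the point conditional. It does not remove it, because a form that conceals the device's name does not conceal values that only one device can generate, and the only text on content points towards providing them.

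A second reply is that the morning value belongs to the strategy under test. The Introduction counts detection of morning hypertension among the advantages of home BP, and the trial asks about value in routine practice. This is a fair cost of the fix. It is small here, because the titration rule uses no diurnal value.

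A third reply is that masking has other weak points: a patient given a home device may mention it to the physician. That is true, and the fix does not close that route. It is no reason to leave an avoidable leak in the form itself.

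A reader might also infer that home-arm titration is undefined, as a separate defect. The documents do not support that. The all-readings average is listed first and is the obvious default, the steps are worded as suggestions, and drug choice is discretionary in every arm. What is missing is a detail, and the fix supplies it in passing.

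**Conclusion.** The point holds as a conditional, minor weakness. Followed on its natural reading, the BP monitoring section would put values in front of home-arm physicians that neither other arm can produce, and this works against the masking claimed elsewhere. It rests on two assumptions: that three averages are meant, and that the form prints them so that they can be recognized. If the form already shows one value, only the wording needs to be aligned.

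Two stronger conclusions are tempting and should not be drawn. One is that physician blinding has failed; the form is not in the documents, so that cannot be known. The other is that the 3-month comparison of 24-hour SBP is biased, or that the 5 mmHg non-inferiority margin is threatened. The documents give no morning-afternoon difference, no rate at which physicians would recognize the arm, and no indication of which way they would then titrate. Neither the direction nor the size of an effect can be derived, and no percentage is offered.

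**What to change.** In the BP monitoring and masking sections, state that:

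- the standardized form shows one SBP/DBP per visit, in the same layout for every arm;
- for home BP this is the mean of all readings on days 2 to 7, and it is the SBP to which the Study protocol's titration steps refer;
- the morning and afternoon averages are stored for analysis and not shown to the treating clinician.

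Check the form in use against this text. If it already prints one value, amend only the home-BP sentence to match. Naming the guiding value while still printing the split would settle which number to use but would leave the masking risk.

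The cost is a few sentences and a form check, with no change to the 84 patients per group. Clinicians lose sight of the morning value, and unblinding through what patients say remains possible.

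### Clinicians see only the allocated device's BP and hypotension has no stated source device, so comparing asymptomatic low BP between arms would partly compare devices

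*Combined protocol and SAP*

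**What the plan says.** **What the clinician sees.** In the combined protocol and SAP, the section *Study protocol* says that at scheduled visits "the corresponding BP will be measured before meeting doctors and provided for clinicians to adjust patients' medication according to practice guideline". The section *BP monitoring: uAOBP, central BP, and home BP* repeats this for the stored readings: "corresponding BP values in each arm will be provided for clinicians to guide their hypertension management". Values reach the physician "through a standardized report form without the knowledge of the used BP monitoring devices".

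**What is measured.** Table 1 ticks uAOBP and central BP at Visits 1-7 with no restriction by arm, and the two are taken simultaneously on opposite arms. For ambulatory BP, "The ambulatory BP of all subjects will be measured at baseline, at 3 months, and at the end of the study". The home device is supplied to the home BP arm.

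**What is blinded.** The outcomes in *Randomization, Outcomes, and Masking* include 24-hour ambulatory SBP and DBP and "change of SBP/DBP measured by uAOBP monitoring, home BP monitoring, or central BP monitoring". The same section says: "Except patient reported outcome and adverse events, the investigators and participants are blinded to all the above outcome variables".

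**What triggers action and recording.** *Study protocol* says: "If low BP (less than 90/70mmHg) or any possible drug related side effects was noted, cautious adjustment of antihypertensive will be done". It does not name the device on which low BP must be noted. Hypotension is a listed side effect within the secondary outcomes. Electrolyte imbalance, renal failure and bradycardia in that list have numeric limits; hypotension does not. The event list in *Data Safety Monitoring* does not name hypotension or a low BP reading.

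**The concern.** Hypotension is one of the harms that a comparison of BP-guided titration strategies needs to report fairly, and the plan's stated aim covers safety as well as effectiveness. A fair comparison needs the event ascertained in the same way in each arm. Here the only pressure in front of the person recording side effects comes from a different device, averaged differently, in each arm. A patient without symptoms whose pressure is low on one device and not on another could be noted as hypotensive in one arm and not in the next, with no difference in the patient. A difference between arms in recorded hypotension, or its absence, could then reflect the measuring method and not the guiding strategy.

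There is also a gap in handling. The trial may hold a low reading on a device that the clinician is not shown, and no section says what happens to it.

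**Working it through.** The plan gives no figure on this point, so there is none to reproduce. The check is to set the sections side by side and then ask whether a size can be derived.

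**1. Ascertainment by arm, if hypotension is noted from the value shown**

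| Arm | Value shown to the clinician | BP readings not shown |
|---|---|---|
| Home BP | Average over 7 days with day 1 discarded | Same-visit uAOBP and central BP; ambulatory BP |
| uAOBP | Same-visit average of 3 brachial readings | Same-visit central BP; ambulatory BP |
| Central BP | Same-visit central estimate | Same-visit uAOBP; ambulatory BP |

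Three arms, three sources, and no common one.

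**2. What does not depend on the device.** The action rule in *Study protocol* has two limbs: low BP, or any possible drug-related side effect. The second limb needs no reading. Adverse events are exempt from the blinding, and dizziness, syncope and injurious fall are recorded in all arms. The arm-dependence is therefore confined to low BP without symptoms.

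**3. Can the size be derived?** If a device's readings are roughly normal with mean m and SD s, the share of visits below a limit L is Φ((L − m)/s). This needs m and s for each guiding device. The plan's only SD, 11 mmHg, is for ambulatory BP, which guides no arm. No between-device difference or spread is given, so the size is not computable.

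**4. Can the direction be derived?** An illustration with assumed inputs shows that it cannot. Take diastolic BP alone with L = 70, uAOBP mean 75 to 85 and SD 10:

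- uAOBP: Φ((70 − 75)/10) = Φ(−0.5) = 31%; Φ((70 − 85)/10) = Φ(−1.5) = 7%.
- Home, modelled as uAOBP plus independent error with mean 0 and SD 5 to 8: s = √(100 + 25) = 11.2 to √(100 + 64) = 12.8. Then Φ((70 − 85)/11.2) = 9% and Φ((70 − 75)/12.8) = 35%.

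Under that model the home arm flags low diastolic BP slightly more often (9-35% against 7-31%). But with m above L, Φ((L − m)/s) falls as s falls. If the multi-day home average is less variable than a single-visit value, the order reverses. The sign rests on the assumed model. The illustration also reads the 90/70 figure as met by the diastolic value alone, which the plan does not say.

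**5. Is a common source available?** Taking Table 1 as it stands, every patient has uAOBP at the 6 post-baseline Visits 2-7 and ambulatory BP at 3 and 12 months. At full enrolment, before dropout, that is 252 × 6 = 1,512 uAOBP assessments and 252 × 2 = 504 ambulatory recordings. These are the data available for a common count, not a measure of harm. Home BP cannot serve, because its device goes to one arm.

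**The case against.** The strongest reply is that guidance by a single device is the intervention. A home-guided patient in routine practice has no simultaneous uAOBP or central reading, and showing one to the clinician before the 3-month endpoint would make the arms more alike in a non-inferiority trial. That stands, and it is why the fix concerns counting and not what the clinician is shown.

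It can also be said that no section requires hypotension to be counted from the allocated device, and that the automated readings are stored digitally, so a common count remains possible at analysis. That is true, but it is not planned. With clinicians recording side effects and seeing only one value, arm-dependent recording is the natural result of the text as written.

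The section *Blood pressure threshold* reports comparable central and brachial values for a type II device. This weakens the contrast between the uAOBP and central arms and leaves the home arm as the more plausible one to differ.

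A reader might infer more than the documents support:

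- *That low BP is acted on only if the arm's own device shows it.* The side-effect trigger and the adverse-event exemption contradict this.
- *That release of a low reading for safety is forbidden.* Withholding is inferred from the sentences on corresponding values and on blinding; no sentence forbids release.
- *That low BP is missed more often in the home arm.* Step 4 of the working shows that the direction is unknown.
- *That the number of readings not shown measures harm.* Such a count would include baseline and final-visit readings and says nothing about how many are low.
- *That the 180/100 entry limit should work as an on-study alarm.* It is a screening exclusion only.

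**Conclusion.** The concern holds in a limited form. Hypotension is a listed safety outcome with no definition and no source device. With only the allocated value shown, asymptomatic low BP would be ascertained by three different methods, and the between-arm comparison would partly compare devices. Symptomatic hypotension can be acted on and recorded in any arm. The primary outcome is not affected by this ascertainment problem, since 24-hour ambulatory SBP is measured in all subjects whatever their arm.

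Size and direction cannot be stated from the documents. The conclusion rests on two readings of the text: that the corresponding value is the only BP the clinician receives, and that clinicians record hypotension from what they see.

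**What to change.** In *Randomization, Outcomes, and Masking* and *Data Analysis and Statistical Analyses*, state that:

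- for the between-arm safety comparison, BP-defined hypotension is counted in all arms from the same stored measurements: uAOBP at Visits 2-7 and ambulatory BP at 3 and 12 months;
- the limit is the protocol's own low-BP figure, once it is clear whether both components or either one must be low, and which ambulatory summary is counted;
- uAOBP and ambulatory counts are shown separately, because uAOBP guides one arm and ambulatory BP guides none;
- clinician-reported symptomatic hypotension is reported separately.

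Confirm at the same time that Table 1's uAOBP ticks apply to every arm. The cost is a little more analysis work, with no new measurement and no change to what the clinician sees.

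Separately, *Study protocol*, *BP monitoring*, *Randomization, Outcomes, and Masking* and *Data Safety Monitoring* must be reconciled on how a low reading on a blinded, non-allocated device is handled. That is for the investigators and the safety board; no threshold, release rule or clinical response is proposed here.
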